1. BACKGROUND

1.1. The fastest growing HIV epidemics globally are driven by injection drug use. Injection drug use is a major vector for HIV/AIDS in seven of 10 world regions, including Eastern Europe and Central Asia (EECA), southeast Asia, the Middle East, Latin America, and Appalachia and other rural areas in the U.S.^{1,2} People who inject drugs (PWID) are disproportionately burdened by HIV, and in regions with HIV epidemics driven by injection drug use, HIV prevalence is over 40% among PWID.³ HIV epidemics among PWID spread due to punitive drug laws, inadequate access to HIV care, and few available interventions.^{3,4} As opioid epidemics continue to increase worldwide, more effective strategies are needed to reduce HIV transmission and HIV-related morbidities.⁵ This proposal addresses the tremendous need for innovative ART adherence interventions for PWID that also provide attention to drug use issues among this population.

1.2. EECA has one of the fastest growing HIV epidemics in the world. EECA is the only region globally where both new HIV infections and HIV-related mortality are increasing.⁶ New HIV infections in the region increased by 57% in 2015, while remaining static or declining in all other global regions.⁶ This rapid increase is occurring in a setting of highly prevalent opioid injection.⁶⁻⁸ In EECA countries, as in many other areas of the world, HIV+ PWID are not adequately treated, thereby undermining treatment as prevention strategies.⁹ In Kazakhstan, the majority of people living with HIV (PLWH) are PWID (52%), and the majority of eligible HIV+ PWID are on ART (87%). However, only 27% of HIV+ PWID on ART are virally suppressed, indicating significant adherence challenges.¹⁰ Studies on ART adherence interventions among HIV+ PWID in developing countries are limited,¹ which is problematic given large HIV epidemics among PWID in these countries.^{3,11} Without evidence-based interventions (EBIs) to promote adherence among PWID an effective response to the HIV epidemic is unlikely. Given that the EECA has among the highest injection drug use rate and prevalence of HIV among PWID in the world,³ the region is an optimal location to develop and adapt adherence EBIs for PWID. Moreover, low threshold interventions using mobile technology and dried blood spot (DBS) testing that are designed for low resource settings in EECA have potential to be implemented and scaled up in resource-constrained rural areas in the U.S. and other countries experiencing heroin epidemics.

1.3. ART adherence is critical to achieving viral suppression and reducing the spread of HIV. Because HIV+ PWID are from high-risk social networks, improving adherence to ART may reduce sexual and parenteral transmission of HIV to the broader community.¹ Although some physicians are reluctant to prescribe ART to PWID,^{1,12-15} studies have found that HIV+ PWID can reach similar levels of ART adherence found among PLWH who have never used illicit drugs, particularly with social support and methadone maintenance treatment.^{1,16} Evidence indicates that the simultaneous combination of ART adherence interventions with linkage to opioid substitution therapy (OST) and needle-exchange programs has a joint effect and provides more positive clinical outcomes and a greater reduction in HIV transmission than individual strategies alone.^{1,17-19} In this project we will integrate referrals to OST and needle-exchange programs into our adapted couple-based adherence intervention.

1.4. New biological assays that measure ART drug levels can provide an objective adherence measure in a clinical setting and could be a useful tool in ART adherence interventions for PWID. ART drug levels in blood provide direct evidence of drug ingestion, but the short plasma half-lives of parent drugs (often hours) results in only an assessment of very recent adherence, thus limiting their applicability in clinical settings. Tenofovir (TFV) is a nucleoside analog that is used in common ART regimens. TFV is phosphorylated in cells to TFV-diphosphate (TFV-DP), which has a longer plasma half-life than the parent drug²⁰ and reflects longer term drug exposure (adherence).²⁰⁻²³ [name] has developed an assay for TFV-DP using DBS, which are easily collected in low resource settings. Furthermore, he is developing a point-of-care (POC) version of the assay that would allow rapid assay of samples collected by clinic providers or pharmacists.^{24,25} Such an assay may provide early warning of viremia and be the basis for clinical feedback for earlier intervention to prevent viral rebound and development of resistant virus. In the proposed project, we will test the feasibility and acceptability of sample collection in AIDS Center clinics in Kazakhstan and will interview HIV+ PWID and healthcare providers about strategies for and acceptability of collecting samples in other community and health system venues.

1.5. A couple-based intervention holds promise for improving ART adherence among PWID. Access to social support from intimate partners is critical in ART adherence among HIV+ PWID.²⁶⁻³⁰ Yet most HIV interventions focus on individuals as a unit of change, ignoring couple dynamics and the important role that partners play in risk behaviors and HIV treatment engagement and adherence.^{31,32} Couple-based interventions have several advantages over individual approaches, including: 1) promoting mutual responsibility in protecting each other from HIV transmission and/or improving each other's health and ART adherence; 2) highlighting the relationship context and its connection to HIV acquisition and disease progression; and 3) creating a safe environment to discuss sensitive topics, such as sexual concurrency, needle-sharing, and medication

adherence.³² Project Renaissance (R01DA022914; PI: [name]), a couple-based HIV and overdose prevention intervention for PWID, was effective in reducing HIV acquisition, HIV risks, and overdose.³³ Intervention effectiveness and high retention achieved in this study demonstrate the feasibility of conducting couple-based adherence intervention research among PWID in Kazakhstan.

In focus groups conducted with 58 HIV+ PWID in Kazakhstan, participants cited partner support as a key facilitator of ART adherence.³⁴ Participants stated that intimate partners provided needed support for dealing with their HIV status in a context where many of them are rejected by their families and experience high levels of stigma and discrimination for being HIV+ and a PWID from the community and healthcare providers as well.³⁴ Despite the desire for a couple-based approach, there is only one couple-based ART adherence EBI (SMART Couples), but it has not yet been adapted for PWID. The proportion of prescribed doses taken within a specified time window, as measured by MEMS Cap, was significantly greater among the intervention participants than control participants at 3 months (change score $b = -13.17$, $p=.028$).³⁵ The four-session SMART Couples intervention was designed to improve ART adherence among HIV+ patients by intervening with both the patient and his/her primary partner in order to foster support from the partner to achieve optimal adherence.³⁵⁻³⁷ While the intervention was shown to be effective in increasing the proportion of prescribed doses taken, its effects were short-lived.³⁵ Therefore, we propose to strengthen this promising and well-developed intervention to make it more relevant for PWID by integrating other existing efficacious adherence intervention strategies for PWID (i.e., directly observed therapy, drug risk reduction components)^{38,39}, incorporating linkage to opioid substitution therapy (OST), and adding new biomedical tools that provide an objective measure of adherence and may provide greater utility in a clinical setting than current adherence monitoring tools (i.e., electronic monitoring devices). The adaptation of an existing, efficacious couple-based adherence intervention strategy for PWID, combined with the integration of efficacious individual-level adherence strategies (i.e., directly observed therapy (DOT)) modified for couples and the incorporation of linkage to drug treatment services and needle-exchange programs could substantially improve adherence among HIV+ PWID, especially in resource constrained settings. Additionally, measuring adherence over time through the use of a mobile app and through new biomedical strategies to measure adherence (i.e., dried blood spot (DBS) tests) could provide a more objective measure of adherence, allowing earlier detection of adherence problems and more timely intervention.

2. STUDY AIMS

AIM 1: Adapt and refine the SMART Couples intervention and identify augmentative intervention strategies guided by the collaborative intervention planning framework⁴⁰ to create an integrated, couple-based ART adherence intervention for HIV+ PWID and their treatment support partners.

AIM 2: Pilot test the resulting couple-based intervention among 66 heterosexual PWID couples in Kazakhstan through a randomized control trial (RCT) to assess the safety, feasibility and acceptability of the intervention and obtain preliminary estimates of adherence outcomes (e.g. electronic monitoring devices, self-reported adherence, viral load) in the intervention arm versus standard of care.

3. STUDY RATIONALE

[figure not shown]
Only 27% of HIV+ PWID on ART in Kazakhstan are virally suppressed, indicating significant adherence challenges.¹⁰ Studies on ART adherence interventions among HIV+ PWID in developing countries are limited,¹ which is problematic given large HIV epidemics among PWID in these countries.^{3,11} ART adherence is critical to achieving viral suppression and reducing the spread of HIV. Without evidence-based interventions (EBIs) to promote adherence among PWID an effective response to the HIV epidemic is unlikely. The adaptation of an existing, efficacious couple-based adherence intervention strategy for PWID, combined with the integration of efficacious individual-level adherence strategies (e.g., the incorporation of linkage to drug treatment services and needle-exchange programs) could substantially improve adherence among HIV+ PWID, especially in resource constrained settings such as Kazakhstan.

4. STUDY DESIGN

4.1. Theoretical Framework. This study is guided by the integration of Behavior Exchange Theory (BET)⁴¹ with Social Action Theory (SAT).⁴² BET posits that couples in high satisfaction relationships will engage more frequently in behaviors perceived as positive or supportive by their partner than will couples in low satisfaction relationships.⁴¹ SAT (the underlying theory of SMART Couples) posits that behavioral change is the result of self-regulation processes, social interdependence, and contextual influences.⁴² Research on social support indicates that the availability of a trusted confidant is a critical factor determining whether people feel they are supported in coping with difficult challenges (i.e., HIV management, ART adherence).⁴² The integration of BET with SAT allows us to analyze relationship satisfaction, self-regulation, and contextual influences to identify processes conducive to sustained support (see Figure 1 above). These theories suggest, and numerous studies indicate,^{32,43-45} that people feel greater support for self-protective behaviors and more confident in their

ability to change if they and a trusted other are able to a) report mutual responsibility for each other's health, b) communicate about their relationship in a safe environment, and c) engage in collective goalsetting and monitoring activities. Manipulating these relationship capabilities in adherence interventions has the potential to effectively increase and sustain ART adherence and reduce risk behaviors (i.e., needle-sharing, drug use, sexual concurrency). This model guides my selection of research questions and methods.

Figure 1: Integrated Behavior Exchange and Social Action Theory

4.2. Study Design Overview.

In the pilot testing phase, 66 HIV+ PWID and their treatment support partners (n=66) will participate in a pilot randomized controlled trial (RCT) of the adapted couple-based intervention developed in the pre-trial phase of the study. Psychologists and intervention facilitators will be trained to deliver the adapted intervention remotely to assess safety, feasibility, acceptability, retention, and preliminary estimates of adherence to directly inform a future, full-scale R01 efficacy trial. Couples will be randomized to the intervention or standard of care (SOC) arms and assessed with repeated measures at four time-points on ART adherence, behavioral outcomes (i.e., drug use, sexual risk behavior), social support processes, and biological measures from baseline to 6 months post-intervention (see **Table 2** below). Electronic monitoring device (EMD) and weekly mobile app data will be collected throughout the intervention and follow-up periods. Due to COVID-19, all study procedures will be conducted remotely.

4.3. Study location and Recruitment Sites. HIV+ PWID will be recruited from the Almaty AIDS Center, which has 1,546 patients on ART, 660 of whom are PWID prescribed ART at least 6 months, 240 of whom are not virally suppressed.⁴⁶ Current AIDS Center patients on ART are 57.6% male and 42.4% female.⁴⁶ The AIDS Center does not currently provide any routine adherence intervention to patients, but recognizes ART adherence as a significant problem and is highly motivated to conduct research and intervention adaptation with us.

4.3.1. Recruitment and Eligibility Screening. Participants will be recruited from the Almaty City AIDS Center. An epidemiologist at the Almaty City AIDS center will review patient records to determine which patients potentially meet eligibility requirements. A list of potentially eligible patients will be given to nurses at the Almaty City AIDS Center. Nurses will call patients to inform them about the study and, for those who are interested, conduct eligibility screening with them. The nurse will obtain consent from eligible participants to be contacted by research staff and provide research staff with the contact information of eligible participants who have consented to be contacted.

[figure not shown]
Research staff will call eligible participants and explain the study verbally in detail, including the purpose of the study and the study procedures (including risks and benefits) and will answer questions to ensure that the patient understands what would be expected of her/him. The RA will then conduct confirmatory eligibility screening and informed consent. If the participant is eligible, the RA will send the participant a Qualtrics link to complete the baseline assessment. The RA will also obtain participant consent to review recent viral load test results from the AIDS Center and medical/research records. Potential participants will be told that participation in this study is completely voluntary and their decision whether or not to participate in this study or provide permission for screening will not affect any medical treatment they are receiving at the clinic or their participation in any other studies.

4.4. Inclusion/Exclusion Criteria

Participant inclusion criteria

We will recruit 66 dyads (n=132) to participate in a randomized control trial of the adapted couple-based intervention. We anticipate we will need to screen 450 individuals to obtain 66 eligible dyads (n=132). Dyads are eligible to participate if

- (1) both partners are ≥ 18 years old,
- (2) both identify each other as their intimate partner, family member, friend, or other person within their social network,

- (3) the relationship has existed at least 3 months,
- (4) both report feeling safe participating with their partner in the study,
- (5) neither reports any severe physical or sexual violence perpetrated by the other partner in the past year,
- (6) both are able to provide informed consent and follow study procedures, and
- (7) both are fluent in Russian.

In addition, the “index case” (partner initially recruited from AIDS Center) must

- (1) be confirmed HIV+ by the AIDS Center,
- (2) have been on ART at least 3 months,
- (3) not be virally suppressed according to the AIDS Center standard (<500 copies/ml), and
- (4) report injecting any drug in the past year.

“Partners” may be HIV- or HIV+ and may or may not be a PWID. Because dyad dynamics may depend on the sex of the “index case”, women will be the “index case” in at least a third of dyads. If both partners meet eligibility criteria, both will provide consent, complete the baseline assessment, and be randomized to study arm.

Participant exclusion criteria

Individuals who do not meet inclusion criteria or who meet any of the following criteria will be excluded from the study.

- (1) unable to provide informed consent,
- (2) unwilling or unable to participate in study procedures,
- (3) any condition that, in the opinion of the principal investigator and research staff, would make participation in the study unsafe, complicate interpretation of study outcome data, or otherwise interfere with achieving the study objectives.

4.5. Study Enrollment. The Baseline Visit will be conducted remotely by phone or computer with participants. At the Baseline Visit, the participants will provide informed consent, be enrolled in the study, complete the baseline assessment through Qualtrics, and self-collect urine and hair samples (if HIV-positive), which will then be mailed to the GHRCCA research staff.

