4.6.2. Intervention Visits (for participants in the intervention arm)

Intervention sessions will be conducted by phone/video call or in-person in the psychologist’s office (post-COVID) at the AIDS Center. The following procedures/assessments will be performed at the intervention visits:

1. The intervention facilitator will verify the participants by name.
2. The intervention facilitator will request **informed consent** to audiotape the intervention session. If both members of the dyad consent, the intervention facilitator will mark that consent was given and the audiorecorder will be turned on.
3. The facilitator will explain the purpose and activities of the day’s session. S/he will go over the EMD adherence data of HIV-positive participants and discuss adherence patterns and challenges with the dyad.
4. The facilitator will conduct the day’s session with the dyad.

All intervention sessions (3 sessions per couple) must be completed within two months of when the first intervention session is conducted.

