6.4.2. Unintended disclosure. Although it is possible that use of mobile apps or having electronic monitoring devices might also result in inadvertent disclosure of HIV status, we have had no such incidents in a current study (R01-MH09557; PI: [name]; NYPSI IRB# 6451) with over 450 participants using an electronic monitoring device for a 12-month period. Moreover, other colleagues who have used mobile apps or electronic monitoring devices in multiple sites with hundreds of patients have also not had any reported unintended disclosures ([name], [name] personal communication). We will take steps to minimize inadvertent disclosure of HIV status from receipt of text message reminders by keeping the text message simple and without any identifying and/or status related information.

6.4.3. Confidentiality breach. Although study sites will make every effort to protect participant privacy and confidentiality, it is possible that participants' involvement in the study, or information collected by the study, could become known to others, and that participants may experience stigmatization or discrimination as a result. We will take the following steps to protect against the risk of a confidentiality breach.

1. All data, including biosamples, assessments, EMD output, and participant files will be labeled only with study identification numbers, and no participant names will be attached to study data.
2. The participant "key" linking study identification numbers with participant names will be kept by the project manager in a password-protected file on a password-protected and encrypted computer. Only the project manager and authorized research staff will have access to this "key". Personal information including participant's name, address and phone number will be stored separately from research data.
3. Electronic data files will be password protected and stored on a secure study server, which requires authentication to access.
4. All paper research data will be kept in locked file cabinets and will be available only to research staff directly involved in this project and institutional personnel for the purpose of routine audits.
5. All study staff will receive training on procedures to protect participant confidentiality and will take all required courses and certification tests. Participants will be told that all data are confidential within the limits of the law.

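### No entry criterion checks that an HIV-positive dyad member's status is known to the other member, or may be disclosed, although intervention sessions review device data jointly

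*Protocol*

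**What the plan says.** **Entry (Protocol 4.4).** The dyad criteria cover age, relationship, its duration (at least 3 months), perceived safety, recent severe violence, consent and language. The relationship criterion is wide: "both identify each other as their intimate partner, family member, friend, or other person within their social network". The safety criterion is that "both report feeling safe participating with their partner in the study". The index case must "be confirmed HIV+ by the AIDS Center". The other member "may be HIV- or HIV+ and may or may not be a PWID".

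**Sessions (Protocol 4.6.2).** Among the listed procedures for the intervention visits, the facilitator will "go over the EMD adherence data of HIV-positive participants and discuss adherence patterns and challenges with the dyad". There are three sessions per couple.

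**Devices.** SAP 3.2.2 says that the electronic monitoring device (EMD) was given to HIV-positive participants. Protocol 4.6.6 says that both arms receive it.

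**Disclosure risk (Protocol 6.4.2).** The section accepts that "use of mobile apps or having electronic monitoring devices might also result in inadvertent disclosure of HIV status". Its reassurance comes from experience with devices and apps, and the mitigation it states is neutral wording of text messages.

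**The concern.** In a dyadic adherence intervention, the other dyad member is one of the people to whom a participant's status can be disclosed. The plan lets that person be a friend, relative or acquaintance of three months' standing and lets either member be HIV-positive. It then places the device data of HIV-positive members on the table in front of both. Prior disclosure cannot be taken for granted in this population: Protocol 1.5 reports that many HIV-positive people who inject drugs in Kazakhstan are rejected by their families and face strong stigma.

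The stake is participant safety. Section 4.7 names safety among the pilot's primary purposes, and 6.4 counts confidentiality breaches and violence as adverse events. Disclosure cannot be undone. The safety monitoring in 4.6.11 (adverse event reports and an exit interview) would detect it only afterwards.

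**Working it through.** The plan states no figure on this point, so the check is a reading of the text.

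1. **Entry criteria.** Searching 4.4 for any mention of knowledge or disclosure of HIV status between members gives 0 of 7 dyad criteria, 0 of 4 index-case criteria and 0 of 3 exclusions: 0 of 7 + 4 + 3 = 14. The one index-case criterion on HIV status concerns confirmation by the clinic, not what the partner knows.

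2. **What device data show.** Because EMDs went to HIV-positive participants (SAP 3.2.2), having EMD data to review marks the holder as HIV-positive. The wording in 4.6.2 is plural and not limited to the index case.

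3. **How often.** The review is a standing item for the intervention visits. With 33 couples and 3 sessions each, that is up to 33 × 3 = 99 joint reviews. This is a ceiling on occasions, not a count of disclosures.

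4. **Whose status is exposed, and when.**
   - *Index case.* The other member is approached as a treatment support partner in an ART adherence study recruiting from an AIDS Center. That largely implies the index case's status at recruitment, before allocation and in either arm. Section 4.3.1 describes calls to clinic patients but sets out no partner-approach step at which disclosure would be checked.
   - *HIV-positive partner.* Partners of either status are eligible, so taking part tells the index case nothing about the partner. Joint review of the partner's EMD data does.

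5. **Whether another safeguard covers it.**
   - Section 6.3 describes blood-sampling risks only.
   - Section 6.4.2 is limited to apps, devices and texts.
   - Section 6.4.3 recognises that study information could become known to others, but its steps concern labelling, storage and access to records.
   - The safety criterion does not mention status.
   - The violence criterion looks back one year and cannot anticipate a reaction to new information.

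None of these requires anyone to ask about disclosure within the dyad.

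**The case against.** The strongest reply is that consent already does this work. Section 4.3.1 has research staff explain the purpose, procedures, risks and benefits before confirmatory screening and consent, so a member unwilling to be disclosed can decline. Staff may also exclude for "any condition that, in the opinion of the principal investigator and research staff, would make participation in the study unsafe". Consent forms are not in the public copy and may describe joint review.

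Much of this stands. A reader might infer that people are asked whether they feel safe before they know what the study involves; the order in 4.3.1 does not support that. For the index case, the support-partner role makes disclosure largely foreseeable. What does not stand is the step from explanation to verification. The protocol does not say that the explanation mentions disclosure through joint EMD review, the discretionary exclusion prompts no question, and consent wording is not a checked entry condition.

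Three other stronger readings are tempting:

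- **That mailed kits reveal status.** Section 4.6.1 describes one kit under a heading for all participants. Section 4.5 limits sampling to HIV-positive members, but no text says what an HIV-negative member is sent or that one member sees the other's kit. This is possible, not documented.
- **That disclosure biases the arm comparison generally.** Disclosure on joining precedes randomisation, and kits and devices go to both arms. Only disclosure at a session of a partner's status not previously known is specific to the intervention arm, and nothing shows that it would cause dropout.
- **That a share of dyads can be put at risk numerically and set against the attrition allowance.** The documents give no disclosure rate, and such a comparison would assume that every affected dyad is lost.

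**Conclusion.** The gap is real and narrow. Followed as written, the plan can reveal an HIV-positive partner's status to an index case who did not know it, through a listed procedure of the intervention, and neither the entry criteria nor 6.4.2 guards against this. The index case's status is a lesser, earlier exposure at recruitment in either arm, which is why the check has to precede partner contact.

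The size cannot be given: the documents state neither how many partners are HIV-positive nor how many are undisclosed. Session exposure is confined to the 33 intervention couples and, among them, to those with an HIV-positive partner unknown to the index case. The conclusion assumes that facilitators follow 4.6.2 as written and that no unseen consent or screening form already imposes the check. It is a participant-safety point that should be corrected; it does not show a biased treatment comparison.

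**What to change.** Add a dyad criterion to 4.4: each HIV-positive member, asked alone, confirms either that the other member already knows their status or that they agree to its becoming known through joint EMD review.

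- **Timing.** Ask the index case before the nominated partner is contacted and the partner at partner screening. Complete both before any kit is mailed.
- **If the answer is no.** Record only that the dyad is not eligible, and give the other member no reason.
- **Section 6.4.2.** Name joint session review as a route of disclosure and say that this criterion controls it.

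The cost is one question per HIV-positive member, one criterion and a sentence in 6.4.2. A few dyads may become ineligible. Accepting agreement as an alternative to prior disclosure avoids restricting the trial to dyads whose status is already shared. The SAP describes randomisation in the past tense; if enrolment has closed, the change belongs in the protocol of the full-scale trial that this pilot is meant to inform.
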